Fluoride has been successfully used to maintain oral health, especially in dry mouth patients. Yet, the kinetics of fluoride in the mouth of older adults, including those with hyposalivation, is poorly understood. Although they need to use fluoride in higher concentrations, such as prescription toothpastes containing 5,000 ppm of fluoride (F), the extent of the effectiveness of using higher fluoride concentrations in hyposalivation patients has scarcely been explored. Even in individuals with normal salivary flow, the use of a 5,000 ppm F rinse does not result in the expected increased retention of fluoride in the mouth [Staub Larsen et al., 2018], suggesting that there is a limit for increasing intraoral fluoride concentration from oral hygiene products when aiming at increasing their retention. This may be due to the limited supply of positively charged cations, such as calcium, to which fluoride could be bound, to be retained for longer periods in the mouth [Vogel 2011]. Alternative approaches aiming to optimize the fluoride retention by previously supplying a calcium source have been developed [Vogel et al., 2006a, 2006b, 2008a, 2008b], but never tested in hyposalivation patients. For instance, the use of a calcium rinse before a fluoride rinse (Ca→F) successfully enhances fluoride retention in the mouth [Souza et al., 2016], under normal salivary flow conditions. This approach could be particularly helpful for hyposalivation patients, by also providing a supply of calcium ions, which are limited due to the low saliva production.

In the present trial, the effect of salivary flow rate (from normal to hyposalivation) on the retention of fluoride in the mouth of older adults after a fluoride rinse will be studied. We hypothesize that although a reduction in salivary flow reduces the rate of clearance of fluoride from the mouth, the lower availability of calcium ions due to the lack of saliva also reduces fluoride retention. Also, the effect using a calcium rinse before the fluoride rinse to increase fluoride retention in the mouth will be tested in older individuals with a range of salivary flow rates. We hypothesize that the increased retention of fluoride observed after a calcium prerinse will be enhanced in individuals with low saliva flow.

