4 STUDY DESIGN

4.1 OVERALL DESIGN

The overall hypothesis of this study is that a calcium prerinse used before a fluoride rinse enhances the retention of fluoride in the mouth. Additional hypothesis to be tested is that the reduction in saliva flow (hyposalivation) reduces the clearance and therefore increases the retention of fluoride in the mouth.

The study will be a single-site, phase 1 clinical trial, with a randomized, blinded (regarding the investigators and laboratory analysts) and crossover design. Two intervention groups will be tested: 1. Rinsing with a fluoride mouth rinse only, based on sodium fluoride at an over-the-counter concentration; 2. Rinsing with the same fluoride mouth rinse as in 1, but after a mouth rinse with calcium lactate (a food additive, previously used to enhance the intraoral fluoride retention [Vogel et al., 2006a; 2006b; 2008a; 2008b; Souza et al., 2016]).

For each volunteer, randomization will be used to determine which of the two intervention groups to be tested first. Volunteers randomized to start the trial in group 1, will test group 2 in the following phase, and vice versa. Dental plaque (primary endpoint) and saliva (secondary endpoint) will be collected for fluoride analysis. Calcium concentration in both samples will also be determined (secondary endpoints).

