9 STATISTICAL CONSIDERATIONS

9.1 Statistical Hypotheses

- **Primary Efficacy Endpoint:**
- Fluoride concentration in dental biofilm
 - Null hypothesis: A fluoride rinse preceded by a calcium rinse is not superior than a fluoride-only rinse in enhancing fluoride concentration in dental biofilm (fluid and solid phases) up to 2 h after mouth rinsing.
 - Alternative hypothesis: A fluoride rinse preceded by a calcium rinse is superior than a fluoride-only rinse in enhancing fluoride concentration in dental biofilm (fluid and solid phases) up to 2 h after mouth rinsing.
- **Secondary Efficacy Endpoints:**
- Fluoride concentration in saliva
 - Null hypothesis: A fluoride rinse preceded by a calcium rinse is not superior than a fluoride-only rinse in enhancing fluoride concentrations in saliva up to 2 h after mouth rinsing.
 - Alternative hypothesis: A fluoride rinse preceded by a calcium rinse is superior than a fluoride-only rinse in enhancing fluoride concentrations in saliva (fluid and solid phases) up to 2 h after mouth rinsing.
- Calcium concentration in dental biofilm
 - Null hypothesis: A fluoride rinse preceded by a calcium rinse is not superior than a fluoride-only rinse in enhancing calcium concentration in dental biofilm (fluid and solid phases) up to 2 h after mouth rinsing.

- Alternative hypothesis: A fluoride rinse preceded by a calcium rinse is superior than a fluoride-only rinse in enhancing calcium concentration in dental biofilm (fluid and solid phases) up to 2 h after mouth rinsing.
- Calcium concentration in saliva
 - Null hypothesis: A fluoride rinse preceded by a calcium rinse is not superior than a fluoride-only rinse in enhancing calcium concentration in saliva up to 2 h after mouth rinsing.
 - Alternative hypothesis: A fluoride rinse preceded by a calcium rinse is superior than a fluoride-only rinse in enhancing calcium concentration in saliva up to 2 h after mouth rinsing.
- Tertiary/exploratory Endpoints:
- Correlation between salivary flow rate and fluoride concentration in dental biofilm
 - Null hypothesis: There is no correlation ($\beta = 0$) between salivary flow rate and fluoride concentration in dental biofilm after rinsing with a fluoride mouth rinse.
 - Alternative hypothesis: There is a correlation ($\beta \neq 0$) between salivary flow rate and fluoride concentration in dental biofilm after rinsing with a fluoride mouth rinse.
- Correlation between salivary flow rate and fluoride concentration in saliva

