9.3 POPULATIONS FOR ANALYSES

For the primary and secondary outcomes, only participants completing the whole study will provide data for the analyses (per-protocol analysis).

For the tertiary outcomes, a modified intention-to-treat analysis will be used; all volunteers completing the fluoride-only mouth rinse treatment will provide data for the correlation analyses, even if they did not complete the other study treatment.

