9.4 STATISTICAL ANALYSES

9.4.1 GENERAL APPROACH

Descriptive statistics: Data of fluoride concentration in saliva and dental biofilm tend to have a not-normal distribution. If that is the case in this study, these data will be presented as the geometric mean

(of log transformed data) and confidence interval (calculated from log transformed data). Data of calcium, if fitting normal distribution, will be presented as means and standard deviations. If not fitting normal distribution, the same approach for fluoride will be used.

Inferential tests: The comparisons between groups will be made using analysis of variance, having the volunteers as statistical blocks (source of variation). This is only to reduce known variability from the error calculation. One-tailed tests will be used to test for superiority of one treatment versus the other. The p-value will be set at 5%.

Before the analysis of variance, the normality of errors will be tested. It is expected that fluoride data is not normally distributed, and therefore a log transformation of data will be performed (which usually is adequate to normalize the data). The same approach will be used for the calcium data.

Besides the groups comparisons, the salivary flow rate will be correlated with the fluoride concentration in dental biofilm and saliva, to help understand the effect of flow rate on fluoride salivary clearance. For that, a regression analysis will be used to correlate the data of salivary flow with fluoride concentration (area under the curve of fluoride concentration over time) in saliva and dental biofilm. A significance level of 5% will be used in this analysis.

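### The low-flow hypotheses in 2.1 and 4.1 point in opposite directions, and the flow regression meant to inform on salivary clearance uses only AUC, which estimates a net association and not clearance

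*Combined protocol and SAP*

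**What the plan says.** - **Rationale (2.1).** After granting that low flow slows clearance, the protocol hypothesises that "the lower availability of calcium ions due to the lack of saliva also reduces fluoride retention".
- **Overall design (4.1).** An additional hypothesis is that "reduction in saliva flow (hyposalivation) reduces the clearance and therefore increases the retention of fluoride in the mouth".
- **Formal hypotheses (9.1).** The test is whether there is a correlation "between salivary flow rate and fluoride concentration in dental biofilm after rinsing with a fluoride mouth rinse", with a parallel statement for saliva. Both are written as β = 0 against β ≠ 0, so neither has a direction.
- **Analysis (9.4.1).** A regression is used to "correlate the data of salivary flow with fluoride concentration (area under the curve of fluoride concentration over time"), in saliva and in biofilm. Its purpose is given as "to help understand the effect of flow rate on fluoride salivary clearance". On error rate: "A significance level of 5% will be used in this analysis".
- **Population (9.3).** "all volunteers completing the fluoride-only mouth rinse treatment will provide data for the correlation analyses". That is at most 20 people.
- **Rank.** Section 3 lists this objective as tertiary/exploratory; the synopsis (1.1) lists the role of hyposalivation as the secondary objective.
- **Data (8.1).** Each rinse visit yields five post-rinse saliva samples (16, 30, 61, 90 and 121 min) and three post-rinse biofilm samples (15, 60 and 120 min). Sections 9.4.2 and 9.4.3 use the individual timepoints only to compare treatments. No decline rate and no flow-by-time term is planned.

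**The concern.** There are two linked problems.

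First, the protocol commits in advance to both signs. Section 2.1 has retention falling with low flow and section 4.1 has it rising. Whichever sign appears, a report could cite a pre-stated hypothesis that it supports.

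Second, the outcome does not match the purpose given in 9.4.1. Clearance is a rate of loss. AUC is a total over time that depends on both the post-rinse level and the rate of loss. Section 2.1 itself describes two influences of low flow that work against each other: slower washout, and less calcium to hold fluoride. If they act on different parts of the curve, the AUC slope can be close to zero while clearance depends strongly on flow. A finding of no correlation could then be taken to mean that flow does not matter to clearance.

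**Working it through.** **Inputs.** Sampling times are from 8.1. The documents give no loss rate and no starting level, so these are assumed: fluoride at time t is C0·exp(−k·t), with C0 = 1 and k = 0.025/min (1.5/h) at normal flow, and smaller k at low flow. The plan gives no figure of its own for the flow analysis, so there is none to reproduce.

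**Step 1: salivary AUC by the trapezoid rule over 16, 30, 61, 90 and 121 min.**
- k = 0.025: concentrations 0.670, 0.472, 0.218, 0.105, 0.049; AUC = 25.76.
- k = 0.0125, same C0: concentrations 0.819, 0.687, 0.467, 0.325, 0.220; AUC = 48.35. Ratio 48.35 / 25.76 = 1.88.

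**Step 2: the C0 ratio at which the AUC does not change.** It equals AUC at normal flow divided by AUC at the lower k with C0 = 1. The final column is that ratio times exp(−121·k_low) / exp(−121·0.025).

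| k at low flow (per h) | Cancelling C0 ratio | Fluoride ratio at 16 min | Fluoride ratio at 121 min |
|---|---|---|---|
| 1.2 | 0.79 | 0.86 | 1.45 |
| 1.0 | 0.67 | 0.76 | 1.83 |
| 0.75 | 0.53 | 0.65 | 2.42 |
| 0.5 | 0.42 | 0.55 | 3.15 |

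In every row the AUC is 25.76, so a regression of AUC on flow sees nothing, yet the curves differ clearly.

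**Step 3: does including the pre-rinse sample matter?** Starting from a near-zero value at time 0 adds a triangle of 8 × C(16 min). For k = 0.025 the AUC is 25.76 + 8 × 0.670 = 31.13; for k = 0.0125 it is 48.35 + 8 × 0.819 = 54.90. The cancelling ratio is 31.13 / 54.90 = 0.57, with a 2.57-fold ratio at 121 min. The pattern is the same.

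**Step 4: biofilm times (15, 60, 120 min).** With k falling from 1.5 to 1.0/h the cancelling ratio is 0.70 and the timepoint ratios are 0.79, 1.16 and 1.91. With k falling to 0.75/h they are 0.57, then 0.69, 1.21 and 2.56.

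**Step 5: what a decline slope sees.** On the log scale, log C = log C0 − k·t, so under this model the slope is −k whatever C0 is. In the 0.53 case the two AUCs are equal, but the slopes are −0.025 and −0.0125 per min.

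**Step 6: does fluoride at 120 min isolate retention?** It is C0·exp(−120·k), again a product. It is unchanged when the C0 ratio is exp(−120·(0.025 − k_low)): 0.37 for k_low = 0.0167 and 0.22 for k_low = 0.0125. It therefore does not separate the components either.

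**Step 7: precision.** By Fisher's z, the smallest correlation detectable with 80% power at two-sided 5% is tanh((1.960 + 0.842) / √(n − 3)), which is 0.59 for n = 20 and 0.67 for n = 15. Full cancellation is not needed for an effect to be missed.

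**Step 8: simulation under assumed values.** Settings: biofilm times, n = 20, k = 1.0/h × exp(0.3x), log C0 = b·x, x = standardised flow, between-person SD 0.4, residual SD 0.2. The regression of log AUC on flow rejects in 62% of runs with a clearance effect alone. When the starting level also rises with flow, it rejects in 26% (b = 0.1), 6% (b = 0.2), 6% (b = 0.25) and 11% (b = 0.3). The log decline from 15 to 120 min picks up the clearance effect in about 100% of runs. That last figure is favourable by construction, because binding was allowed to act only on C0.

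**The case against.** The strongest reply is that section 3 does not ask for mechanisms. It asks how hyposalivation bears on fluoride retention up to 2 h, with a correlation as the endpoint. That is a net question, and AUC answers it. Section 9.4.1 says only that the regression should help in understanding clearance, and 9.1 tests β without direction, so the clash between 2.1 and 4.1 alters no calculation. This stands. A reader might infer that the hyposalivation objective cannot be answered from the planned test; the documents do not support that.

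Three further points also stand.

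- If 2.1 and 4.1 are read as net predictions, a clearly non-zero slope would favour one over the other, so the test is not uninformative about them. If 2.1 is read only as naming two competing influences, it still does not match 4.1, which names one influence and one direction.
- There is not a single AUC. Saliva and biofilm each have one, and biofilm is measured in fluid and solid phases. Contrasting them could give indirect clues, although no such comparison is planned and each AUC still combines level and loss.
- Identifying binding with C0 and clearance with k is a modelling choice made here. Sections 2.1 and 3 describe bound fluoride as held longer and released over time, so weaker binding could also alter the decline rate. The salivary decline slope may therefore partly reflect release from bound reservoirs.

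What the reply does not remove is the mismatch between the clearance purpose in 9.4.1 and an outcome that is not a clearance measure.

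**Conclusion.** The point holds in a limited form. Sections 2.1 and 4.1 state opposite net expectations, and the only planned flow analysis is a regression of AUC, one per matrix, which estimates the net association and not the clearance that 9.4.1 says it should illuminate. Opposing changes in level and decline rate can cancel in it. In the illustration, equal AUCs go with 1.45- to 3.15-fold differences in salivary fluoride at 121 min.

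These sizes rest on an assumed single-exponential decline, an assumed 1.5/h at normal flow, and starting levels chosen to cancel exactly. The documents give no kinetics, so they show what is possible, not what is likely. It would go too far to conclude that cancellation is expected.

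The consequence is confined to an objective ranked tertiary in section 3 and secondary in the synopsis. The primary endpoint and the treatment comparison are untouched. The change is worth making because it is nearly free and is best specified before the sign of the slope is known.

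**What to change.** 1. Reconcile 2.1 and 4.1 into one hypothesis, or declare the direction open, in line with the two-sided test in 9.1.
2. In 9.4.1, keep the AUC regressions and label them as estimates of the net association between flow and fluoride.
3. Add an exploratory regression on salivary flow of each participant's log-linear salivary fluoride decline slope over 16 to 121 min at the fluoride-only visit. A flow-by-time term in a mixed model of log salivary fluoride is an equivalent choice. Name the flow measure used, since 8.1 collects both unstimulated and stimulated flow and 9.4.1 does not say which is meant.
4. State that a null AUC slope means no net association was detected and does not show that flow has no effect on clearance.
5. Do not present biofilm fluoride at 120 min as isolating retention. Note that the decline slope may include release from bound reservoirs and that loss before 16 min is not observed.

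Cost: SAP wording and one more exploratory estimate, in at most 20 participants, from samples already scheduled. It should be reported without confirmatory claims.

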9.4.2 ANALYSIS OF THE PRIMARY EFFICACY ENDPOINT(S)

Fluoride concentration in dental biofilm (primary efficacy endpoint) will be determined from the samples collected at baseline and 15 min, 60 min and 120 min (± 5 min) after rinsing with the assigned mouth rinse(s). The concentration at each individual timepoint will be compared between the two intervention groups. Also, the area under the curve of fluoride concentration in dental biofilm versus time will be calculated. This single measurement of fluoride bioavailability overtime after the mouth rinse(s) will be compared between the two intervention groups.

Each set of data will be checked for normality of errors. If the data is not normal, it will be log-transformed. An analysis of variance will be conducted, considering as factors the participant (experimental block) and the treatment. The use of the participant as a source of variation aims solely to reduce unknown variability in the error. An alpha level of 5% will be used to determine significant differences between the two groups.

In case data were log-transformed to fit the statistical analysis, their geometric means and confidence intervals (calculated from the log-transformed data) will be presented.

If data is missing from one of the intervention groups, the rest of the participant data (from the other intervention) will be excluded from the analysis.

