3 OBJECTIVES AND ENDPOINTS

OBJECTIVES	ENDPOINTS	JUSTIFICATION FOR ENDPOINTS
Primary		
Determine the benefit of using a calcium rinse, before a fluoride rinse, to enhance fluoride retention in dental biofilm of individuals with hyposalivation.	Fluoride concentration in dental biofilm (fluid and solid phase) up to 2 h after rinsing with fluoride.	Dental biofilm can take up fluoride and release it for prolonged periods of time, like the hours in between oral hygiene procedures.
Secondary		

OBJECTIVES	ENDPOINTS	JUSTIFICATION FOR ENDPOINTS

Determine the benefit of using a calcium rinse, before a fluoride rinse, to enhance fluoride retention in saliva of individuals with hyposalivation.
	
 1. Fluoride concentration in saliva up to 2 h after rinsing with fluoride. 2. Calcium concentration in dental biofilm (fluid and solid phase) up to 2 h after rinsing with fluoride. 3. Calcium concentration in saliva up to 2 h after rinsing with fluoride. 	
 1. Salivary fluoride can be considered as a surrogate measure of fluoride availability in the mouth, because from saliva fluoride from rinses gets to dental biofilm. 2. Since a calcium rinse will be used in one of the treatments in this study, determination of calcium concentration in dental biofilm will be made to identify potential sources of fluoride retention (e.g. fluoride bound to calcium ions, calcium fluoride precipitation). 3. Salivary calcium can be considered as a surrogate measure of calcium availability in the mouth; since a calcium rinse will be used in one of the study treatments, salivary calcium will be determined.
Tertiary/Exploratory		

Determine the role of hyposalivation on the retention of fluoride in the mouth after a fluoride rinse
	
 1. Correlation between salivary flow rate and fluoride concentration in dental biofilm up to 2 h after a rinse. 2. Correlation between salivary flow rate and fluoride concentration in saliva up to 2 h after a rinse. 	
The correlation between salivary flow rate and fluoride in dental biofilm and saliva will be investigated to estimate how the flow rate affect these variables.

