9.2 SAMPLE SIZE DETERMINATION

Data from Souza et al., 2016, using rinses similar to be used in this study, were used in sample size calculation. In that study, analysis of fluoride concentration in dental biofilm 10 h after using the rinses was available. (Note that the expected differences between the groups up to 2 h after the mouth rinsing are expected to be bigger, as saliva production overtime tends to clear all substances from the mouth).

Considering an 80% power to detect differences at the 5% significance level, an estimated sample size of 15 was determined (Stata/SE 15.1 for Mac). The sample size was increased to 20 subjects considering an attrition of 30%.

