9.4.3 ANALYSIS OF THE SECONDARY ENDPOINT(S)

Fluoride and calcium concentrations in saliva (secondary endpoints) will be determined from the samples collected at baseline and 16 min, 30 min, 61 min, 90 and 121 min (± 5 min) after rinsing with the assigned mouth rinse(s). The concentration at each individual timepoint will be compared between the two intervention groups. Also, the area under the curve of fluoride and calcium concentration in saliva versus time will be calculated and compared between the two intervention groups.

Calcium concentration in dental biofilm (primary efficacy endpoint) will be determined from the samples collected at baseline and 15 min, 60 min and 120 min (± 5 min) after rinsing with the assigned mouth

rinse(s). The concentration at each individual timepoint will be compared between the two intervention groups. Also, the area under the curve of calcium concentration in dental biofilm versus time will be calculated and compared between the two intervention groups.

Each set of data will be checked for normality of errors. If the data is not normal, it will be log-transformed. An analysis of variance will be conducted, considering as factors the participant (experimental block) and the treatment. The use of the participant as a source of variation aims solely to reduce unknown variability in the error. An alpha level of 5% will be used to determine significant differences between the two groups.

In case data were log-transformed to fit the statistical analysis, their geometric means and confidence intervals (calculated from the log-transformed data) will be presented.

If data is missing from one of the intervention groups, the rest of the participant data (from the other intervention) will be excluded from the analysis.

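### The primary biofilm-fluoride hypothesis gets eight post-rinse tests, each one-tailed at 5%, with no rule for which decides; if any one counts, the false-claim rate is about 11–29%

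*Combined protocol and SAP*

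**What the plan says.** Section 3 defines the primary endpoint as "Fluoride concentration in dental biofilm (fluid and solid phase) up to 2 h after rinsing with fluoride". Section 9.1 gives it one null and one alternative hypothesis, the alternative being that the calcium-then-fluoride rinse is "superior than a fluoride-only rinse in enhancing fluoride concentration in dental biofilm (fluid and solid phases) up to 2 h after mouth rinsing". Section 8.1 separates the two phases by centrifugation and assays each.

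Section 9.4.2 lists biofilm samples at baseline, 15, 60 and 120 min, and then says "The concentration at each individual timepoint will be compared between the two intervention groups. Also, the area under the curve of fluoride concentration" is to be calculated. Of the AUC it says "This single measurement of fluoride bioavailability overtime after the mouth rinse(s) will be compared between the two intervention groups". Each comparison uses an analysis of variance with participant and treatment as factors, at an alpha of 5%. Section 9.4.1 adds "One-tailed tests will be used to test for superiority of one treatment versus the other. The p-value will be set at 5" per cent.

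Section 9.2 sizes the trial on a single comparison: "Considering an 80% power to detect differences at the 5% significance level, an estimated sample size of 15 was determined". This was raised to 20 for 30% attrition.

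No section names a deciding measure, a testing order, an either-phase or both-phases rule, or a multiplicity adjustment.

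**The concern.** The plan sets up a formal superiority claim, with a named primary endpoint, stated hypotheses, a 5% level and 80% power. It then attaches several full-alpha tests to that claim without saying what pattern of results rejects the null. Two analysts following the plan could look at the same data and reach opposite primary conclusions. One might accept a significant 15 min result in biofilm fluid; the other might require AUC in both phases. The rule could also be settled once the results are known.

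The gap affects trial conduct too. Section 10.1.2 allows the study to stop once the primary endpoint has been met, and that cannot be determined without a rule.

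**Working it through.** **Counting the tests.** Post-rinse times: 3 (15, 60, 120 min). AUC: 1. Phases: 2. So (3 + 1) × 2 = 8. Section 9.4.2 does not itself mention phases; the factor of 2 comes from Sections 3, 8.1 and 9.1. The baseline comparison is left out because a pre-rinse difference cannot support a claim about the 2 h after rinsing. Read literally, Section 9.4.2 could include it, giving (4 + 1) × 2 = 10.

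**The plan's own figure.** The documents state no family-wise error rate to reproduce. The sample size of 15 cannot be reproduced either, because Section 9.2 gives no effect size, SD or sidedness. Solving backwards for a paired t-test with n = 15 and 80% power gives a standardized paired difference of 0.675 (one-sided 5%) or 0.778 (two-sided 5%). Enrolling 20 and losing 30% leaves 20 × 0.70 = 14 completers.

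**Test statistic.** With two treatments and participants as blocks, the analysis of variance is equivalent to a paired t-test: t = mean difference ÷ (SD of differences ÷ √n). At n = 15 a one-tailed 5% test rejects when t exceeds 1.761 (14 df).

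**Simple ceiling.** For eight independent tests, 1 − 0.95⁸ = 33.7%. This overstates the rate, because each AUC is built from the same timepoints.

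**Simulation with no treatment effect.** Multivariate-normal paired differences, n = 15, trapezoid AUC with and without the pre-rinse sample as its first point. Correlations over time and between phases were each set to 0, 0.5 and 0.9. These are assumptions.

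| Rule that could be read into the plan | False-claim rate |
|---|---|
| Any one of the 8 tests | 11–29% (21% at 0.5/0.5) |
| AUC in either phase, unadjusted | about 7–10% |
| Same measure significant in both phases | 0.5–10% |
| Any measure significant in each phase | 0.6–11% |
| AUC in both phases | 0.2–3% |
| AUC with Holm over the phases | 3.5–5.0% |

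For any one of the 8, correlations of 0.95 still give about 9%, and n = 20 agrees with n = 15 to within about 1 percentage point. Counting baseline (10 tests) gives about 12–36% for correlations from 0.9 to 0.

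**When one phase truly responds and the other does not.** A false both-phases claim then needs only one of the four tests in the null phase to be significant. As the effect in the responding phase grows, the rate approaches 8–16%. Requiring AUC in both phases keeps it at or below 5%, because the null phase then has a single 5% test.

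**Power under a stated rule.** Ranges run over phase correlations 0 to 0.9, with the same effect in each phase.

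| Effect and n | Holm, at least one phase | Both phases required |
|---|---|---|
| 0.675, n = 14 | 72–88% | 60–72% |
| 0.675, n = 15 | 75–90% | 64–75% |
| 0.675, n = 20 | 87–97% | 80–87% |
| 0.778, n = 15 | 85–96% | 79–85% |

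The zero-correlation ends can be checked by hand at 0.675 and n = 15. Both phases: 0.80² = 64%. Holm: one test at 2.5% has power 68.2%, so 1 − (1 − 0.682)² = 90%. If only one phase responds, Holm has about 68%.

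**The case against.** The strongest reply is that the plan never says any one result counts. The hypothesis in Section 9.1 names the phases jointly, which suggests that both must succeed. The AUC is described as a single measurement, fits an endpoint running to 2 h, and is the summary used for the regressions in Section 9.4.1, so it may have been meant to decide. On those readings the no-effect error rate is lower: 3.8% at 0.5/0.5 if some measure must succeed in each phase, and at most about 3% if AUC must succeed in both. The 29% end also needs zero correlation between fluid and solid fluoride, although both come from the same pooled sample. Finally, this is a phase 1 crossover in 20 people with concentration endpoints.

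Much of this is fair. About 21% is a more credible central figure than 29%, and the rate does depend on the rule. But neither favourable reading is written down, and Section 9.4.2 introduces the AUC as an addition to the timepoint comparisons. If AUC does decide, the phase question remains: either phase unadjusted gives about 7–10%. If both phases must succeed on some measure, the 8–16% scenario remains. The small scale does not answer a plan that itself frames the question as a superiority test at 5%.

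**Conclusion.** The concern holds, and it should be resolved before the data are analysed. The finding that the rejection rule for the primary hypothesis is undefined needs no simulation. The size depends on which rule is read in: about 11–29% if any one of eight results counts, about 7–10% if AUC in either phase counts, and no guarantee of 5% if some measure must succeed in both phases. These figures assume normally distributed paired differences, n = 15 and correlations from 0 to 0.9. The power figures also rest on an effect solved back from Section 9.2. That section expects larger differences up to 2 h than in the 10 h data it used, so they are illustrations rather than predictions.

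**What to change.** In Section 9.4.2:

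- Name the AUC of biofilm fluoride to 120 min as the single primary measure. State its start time (pre-rinse or 15 min) and that it is log-transformed under the plan's existing rule.
- State one phase rule: Holm across fluid and solid, so that a claim is made for each phase that passes, or success in both phases at one-tailed 5%.
- Report the 15, 60 and 120 min comparisons as supportive, with confidence intervals. Use the baseline comparison only to check balance or carryover.

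Another measure could serve as primary, provided it is fixed in advance. Keeping all eight tests as alternatives would need 0.05 ÷ 8 = 0.00625 each under Bonferroni.

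No extra participants or samples are needed. The cost is power. If the 15 came from a one-sided calculation, the both-phases rule has 60–72% power at 14 completers and reaches 80% at every assumed correlation only if all 20 complete. Holm has 72–88% for at least one phase at 14 completers. Section 9.2 should state its effect size, SD and sidedness, and give the power under the chosen rule.

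As a clerical edit, Section 9.4.3 labels biofilm calcium a primary endpoint under the secondary-endpoint heading ("Calcium concentration in dental biofilm (primary efficacy endpoint) will be determined from the samples"). Sections 1.1, 3 and 9.1 list it as secondary.
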